7.1 Study Subjects

7.1.1 Disposition of Subjects

A STROBE flow diagram will be used to describe the disposition of study subjects for analysis of the primary objective. This flow diagram will keep track of the number of patients for the following categories: enrolled, withdrawn, death, exited, > 90 days without transmitting device data, completed at least 1 survey, completed 75% of all tasks.

7.1.2 Clinical Investigation Plan (CIP) Deviations

Due to the nature of this study, site level deviations will not be collected, only Study level deviations will be collected by the sponsor. Patients who do not meet inclusion/exclusion criteria will be excluded from analysis.

7.1.3 Analysis Sets

All patients who enroll and successfully install the study app will be included in the full analysis set. Additional data inclusion/exclusion constraints specific to an objective are specified within the analysis methods.

7.2 General Methodology

Data from all enrolled patients will be summarized, but analysis of each objective will account for the completeness of the data in the context of addressing the objective. In particular, patients contributing to objectives that are modeling HCU-based outcomes should have provided a minimal amount of

DEFINE AFib Statistical Analysis Plan Form Medtronic Revision [2.0] Page 11 of 25

information to ensure that HCU data has been made available. This can be accomplished through the completion of monthly and triggered surveys or by sharing EHR information through the study app or via sites. Complete device data should be available for all patients. Patients should have regularly transmitted CareLink data throughout follow-up. If no device data or limited device data is available from a patient, that patient will need to be either excluded from analysis or follow-up will need to be limited to the period of time up until device data is not available.

For patients who enroll at the time of LINQ ICM implant, all follow-up data will be analyzed from the time of implant, if the patient completes all baseline enrollment tasks within 7 days of the LINQ ICM implant. Baseline enrollment tasks include enrollment, signing their consent, and completing all baseline survey questionnaires (patient profile, medical history, medication history, EQ-5D-5L, AFEQT). For patients who are enrolled more than 7 days after the LINQ ICM implant or who completed enrollment tasks more than 7 days post-implant, follow-up will begin when all baseline enrollment tasks have completed.

The final data analysis will be performed by a Medtronic statistician or designee. The timing of the final analysis will be determined during the interim analysis (see Section 7.8). Any change to the data analysis methods described in the protocol will require an amendment only if it changes a principal feature of the protocol. Any other change to the data analysis methods described in the protocol, and the justification for making the change, will be described in the clinical study report.

7.3 **Center Pooling**

[figure not shown]
The primary objective of this study is to develop risk prediction models and not to compare two arms via a hypothesis testing. Thus, poolability analysis will not be performed in this study. However, the following will be done to reduce the effect of possible heterogeneity across sites:

- When randomizing patients into training/validation/test datasets, the randomization will be stratified by sites
- Predictive models will include site characteristics (e.g. region, size healthcare system) and patient characteristics as input of the model
- Error analysis will be performed to identify cohorts with higher prediction error and diagnose the root cause (e.g. heterogeneity across sites) behind these errors
- CRFs will have the definition of the following events to guide center coordinators to identify them:

Table 2: Healthcare Utilization Definitions

HCU	All inpatient hospitalizations, outpatient hospital encounters, emergency department visits, clinic visits, urgent care visits, rehab center or other care location interactions (including remote visits)
-----	--

Revision [2.0] Page 12 of 25

CV-related HCU	A healthcare utilization relating to the heart and the blood vessels or the circulation (e.g., atrial fibrillation, myocardial infarction, stroke, peripheral vascular disease, heart failure).
AF-related HCU	HCU related to AF, suspected AF, AF treatment, or complications related to AF (including bleeding and drug toxicity as determined by treating clinician.
HF-related HCU	A healthcare utilization related to worsening heart failure signs and symptoms (as determined by treating clinicians) such as (but not limited to) hypervolemic and hypovolemic status requiring the administration, alteration, adjustment, or augmentation of HF therapy (diuretics, inotropes and/or vasodilators etc.) or the utilization of ultrafiltration devices.
Hospitalization	A therapeutic inpatient hospitalization (excludes outpatient and emergency room visits) lasting greater than or equal to 24 hours.
Non-hemorrhagic stroke	Rapid onset of a focal or global neurological deficit or other neurological signs/symptoms consistent with stroke; whereas focal, global cerebral or spinal dysfunction was NOT caused by a non-traumatic intraparenchymal, intraventricular, or subarachnoid hemorrhage, as determined by the treating clinician.
Systemic embolism	An embolus resulting in clinical and objective evidence of sudden loss of end organ perfusion.
TIA	New focal neurological deficit with rapid symptom resolution (usually 1 – 2 hours), always within 24 hours without tissue injury (based on neuroimaging) as determined by the treating clinician.

7.4 Handling of Missing, Unused, and Spurious Data and **Dropouts**

Unless otherwise specified in the evaluation methods, data points with missing values will not be included. The percent of missing data will be tracked of be part of data quality.

7.5 Adjustments for Multiple Comparisons

No adjustment for multiple comparisons will be made. This is a single arm study, where the goal in the primary objective is to develop predictive models and not perform hypothesis testing.

Revision [2.0]

Page 13 of 25

Demographic and Other Baseline Characteristics

Descriptive statistics will be used to summarize baseline and demographic characteristics. For categorical variables (e.g. sex), counts and percentages will be employed, while for continuous variables (e.g. age), means, standard deviation, quartiles, minimum, and maximum will be provided. These statistics will be provided for all enrolled subjects and also stratified by LINQ device model.

7.7 **Treatment Characteristics**

This section does not apply since no treatment effect is being measured in this study.

Interim Analyses 7.8

An interim analysis was initially planned to be performed when there were observed 500 thousand patient-days OR when it had been 16 months since 1st enrollment (whichever comes first). Due to a transition from CIP V3 to CIP V4 (and associated app infrastructure changes) near the time of the planned interim analysis, in addition to slow initial enrollment, the interim analysis timeline was updated to occur within 2 years of the 1st enrollment. The objective of this interim analysis will be to reassess the assumptions and determine if the sample size or follow-up duration of the study needs to be adjusted. Based on the interim analysis, details of how the study objectives will be analyzed (e.g., types of statistical models used) are subject to revision.

Evaluation of Objectives

7.9.1 Primary Objective

The primary objective require development of risk-prediction models for various endpoints using different data source combinations. This section describes a general framework that will be used to develop these models.

Prediction models

For each endpoint, two types of prediction modeling will be considered: one focusing on short term predictions and other on long term predictions. For both prediction modelling types, the following machine learning (ML)/artificial intelligence (AI) methods might be considered (but not limited to):

- Tree Boosting
- Temporal Convolutional networks feedforward neural network (TCN FFNN) (similar approach presented in Catling & Wolff (2020))

Dataset split

DEFINE AFib Statistical Analysis Plan Revision [2.0] Page 14 of 25 Medtronic

Predictive modelling requires the original data to be split into three smaller sets, one for training, one for validation and one for testing. The original data will be randomly split into those three datasets with 70%, 10% and 20% of patients in the training, validation, and testing datasets, respectively. A patient will only contribute data to one of the 3 datasets. To reduce impact of possible heterogeneity across sites, patients and LINQ model, randomization will be stratified by sites, LINQ indication, and LINQ model. Lastly, the testing dataset will only be used after the models under consideration have been trained and validated.

Data format

All predictive models will be trained using similar labeled examples. In particular, at a prediction time point **t** a patient **i** generates a labeled example (hereinafter referred as sliding window) which will be composed of the all features considered as relevant to the clinical endpoint (e.g. LINQ device data, EHR data, etc.) collected between **(t-b)** and **t**, and a binary label indicating if that patient had the clinical event of interest between time points **t+l** and **(t+l+w)**. Figure 1 illustrates the sliding window concept at time **t**. Notice a patient will provide multiple sliding windows.

[figure not shown]

Figure 1: A sliding window at time t is composed of all relevant features values observed from the most recent b days and a binary label indicating if event occurred between t+l and t+l+w. The rationale of the parameter l is to give leading time to the physicians to prevent an event for a patient with high risk of having that event between t+l and t+l+w

Data transformations

All continuous variables will be centered and scaled. Categorical variables will be converted to into one-hot vectors.

Handling missing data

[figure not shown]
Due to the various types of data sources, handling missing data will depend on the requirements of the predictive model and on the data missing patterns observed in the training data. Thus, the decision on

DEFINE AFib Statistical Analysis Plan Form Medtronic Revision [2.0] Page 15 of 25

the methods to be used for handling missing data will be left to the discretion of the statistician/data scientist during the model development phase. However, this decision will be made prior of using the testing data.

Undersampling/Oversampling

Likely the training dataset will have many more instances (i.e. sliding windows) where a clinical event is not observed. Thus, random undersampling/oversampling methods might be needed to build the training dataset. Notice that these approaches will **not** be used to build the validation and test datasets.

DEFINE AFib Statistical Analysis Plan Form Medtronic Revision [2.0] Page 16 of 25

Training model

All models under consideration will be training with the goal of minimizing the cross-entropy loss function.

Tuning

Hyperparameters b, I and w will be determined via grid search algorithm using the validation set and the Area Under Receiver Operating Characteristic (AUROC) curve as the metric to be maximized. Finite set of reasonable values for b, I and w will be set during the exploratory data analysis.

The tuning approach for hyperparameters associated with the training model process (e.g. number of epochs, batch size, learning rate, optimizer, etc.) will be left to the discretion of the statistician/data scientist.

Testing

After all models have been trained and tuned, all final models (i.e. for each clinical endpoint and prediction modeling strategy) will be fitted to the testing dataset resulting in a prediction of each patient's individual probabilities of having the clinical event in the predictive window (i.e. between t+l and t+l+w). More specifically, all models will generate risk prediction (for the clinical event they were designed to predict) for each patient at each day (starting at the bth). The true binary values and the corresponding prediction risk scores will be used to compute the area under the receiver operating characteristic (AUROC), sensitivity, specificity, negative predictive value (NPV) and positive predictive value (PPV). Bootstrapping will be used to compute 95% CIs for these performance metrics.

For each outcome, the performance of the risk prediction models will be presented in contrast to the performance of comparable clinical practices. However, as a guideline, the following scale might be used to help choose the adjective to refer the performance of each model:

AUROC ≤ 0.5: fail

DEFINE AFib Statistical Analysis Plan Form Medtronic Revision [2.0] Page 17 of 25

0.5 < AUROC ≤ 0.6: poor

0.6 < AUROC ≤ 0.7: fair

[figure not shown]
0.7 < AUROC ≤ 0.8: good

[figure not shown]
0.8 < AUROC ≤ 0.9: great

[figure not shown]
AUROC > 0.9: excellent

[figure not shown]
Determination of Subjects/Data for Analysis

Subjects in the full analysis set who have completed all enrollment surveys will be included in the primary objective analysis. Subject follow up might be limited by lack of device information.

[figure not shown]

[figure not shown]

DEFINE AFib Statistical Analysis Plan Form Medtronic Page 20 of 25 Revision [2.0]

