50% of our cohort to provide complete data. In such a scenario, a 5,000 patient cohort would be sufficient for modeling health care utilization (1,175 events, 525 AF-related) but would be insufficient for modeling ischemic stroke or for modeling outcome events by smaller subgroups.

A planned interim analysis will be performed in which we will re-assess these assumptions to determine if the sample size or follow-up duration of the study needs to be adjusted.

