4.1 Primary Objective

To evaluate whether summary and episodic measurements collected by market-released LINQ ICMs are able to predict increased AF-related healthcare utilization (HCU)

Endpoint: Confirmed healthcare visit in the inpatient hospital, outpatient hospital, clinic/office, emergency department, or other care location (including remote visits) where AF was a reason or suspected reason for healthcare interaction

[figure not shown]
Investigation Plan 5.

DEFINE AFib is an observational, post-market clinical study intended to leverage machine learning to evaluate the association between complex patterns of device-detected AF and elevated healthcare utilization, reduced QoL and specific clinical outcomes in patients with a LINQ ICM. These data will improve the business understanding of how data from the LINQ ICM can be used to guide the management of patients with AF.

This study is expected to be conducted at approximately 30 centers in the United States, and it will enroll approximately 5,000 patients (see section 13.1 of the CIP). Study subjects will be followed for up to 5 years, until study closure, or until their LINQ ICM either completes its service life or is explanted, upon which time they will no longer be followed. Study closure may occur when Medtronic requirements have been satisfied per the CIP and/or following a decision by Medtronic or applicable external parties (i.e. institutional review board (IRB) or regulatory authority) to discontinue the study.

Revision [2.0]

Page 7 of 25

Enrollment is anticipated to last for up to 3 years. The estimated total study duration is up to 7 years, representing a three-year enrollment period and up to 5 years of follow-up for all patients.

Inclusion Criteria

- Patients with a Reveal LINQ or LINQ II ICM who have a self-reported history of AF and who have received an ICM for the following device logged indications, categorized into the following groups:
 - o **Stroke**: Cryptogenic stroke indication
 - o **AF management**: AF management and post-ablation management indications
 - Suspected AF: Suspected AF and palpitations indications
- Individual access and ability to use an Apple iPhone® compatible with Medtronic's research app (iOS v. 13.X or higher)
- Patient is willing and able to comply with the protocol, including CareLink transmissions (requires
 adequate connectivity), remotely administered instructions, and remote survey participation
- Patient is 22 years of age or older

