		•	AFEQT	•	Static	•	eConsent completed	•	Starting at enrollment and then monthly (every 30 days +/- 2 days**)	•	14 days post issuance

Revision [2.0]

Page 9 of 25

[figure not shown]
Healthcare Utilization	• HCU	Dynamic	Starting 30 days after enrollment or first triggered event	Starting 30 days after enrollment and then monthly (30 days +/-5 days*) (+/-2days**) (For triggered surveys, including healthcare facility geofence and daily AF burden from CareLink, consult CIP for details) HCU survey should always be deployed with Symptom and Symptom Severity Survey	7 days post- issuance
Symptom and Symptom Severity	MAFSI and modified EHRA symptom severity	Dynamic	Starting 30 days after enrollment or first triggered event	Starting 30 days after enrollment and then monthly (30 days +/- 5 day*)(+/-2days**) (For triggered surveys, including healthcare facility geofence and daily AF burden from CareLink, consult CIP for details) Symptom and Symptom Severity survey should always be deployed with HCU survey	7 days post issuance
Medication	• SMAQ	Static	• Starting 90 days after enrollment (+/-2 days**)	 Starting 90 days after enrollment and then every 3 months (every 90 days +/-2days**) 	30 days post- issuance
• Patient App	Patient impact	Static	Starting 6 months after enrollment (180 days +/- 2 days**),	Starting 6 months after enrollment and then every 6 months (every 180 days +/-2 days**)	90 days post- issuance

6. Determination of Sample Size

A retrospective analysis of the Optum EHR deidentified database (2007-2019), linked to the Medtronic CareLink database of insertable cardiac monitoring (ICM) devices, suggests that in a cohort of 5,000 patients from the intended population of ICM patients, 600 (12%) will have at least one ischemic stroke event and 2,350 (47%) will have at least one healthcare utilization in a five-year follow-up period. Of the healthcare utilization events, 1,050 (21%) will be AF-related. It is expected there will be approximately 5.2 million follow-up days. Given the large number of follow-ups, the ratio of events to follow-up days is extremely rare. Traditional classification approaches (CART, random forest) require under/oversampling

Revision [2.0]

Page 10 of 25

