methods and control parameters for adequate convergence. In the retrospective analysis, the target window was defined as the five days prior to an event (thereby over-sampling events by a factor of five) and then under-sampled controls to a 1:1 ratio with over-sampled cases to create a balanced data set. Setting a minimum node size of 80 patients and requiring the minimum node size to range between 2% and 5% of balanced data, adequately converged to results. The undersampling and model fitting exercise were repeated 100 times to bootstrap an estimate of variable importance for each variable in the model. Using this methodology for convergence and estimation, a minimum of 160 (80/0.05/10) to 400 (80/0.02/10) events are needed for analyzing predictor variable influence and 320 to 800 events for creating a prediction algorithm that requires training, validation, and test partitions as part of its methodology. This latter range is sufficient for deep learning approaches (e.g., LSTM autoencoder, CNN classification network) for predicting extremely rare events.

A minimum of 320 to 800 events implies a 5,000 patient cohort is minimally sufficient for algorithm development. This, however, assumes patients enroll immediately after implant and does not consider attrition. Moreover, this analysis showed that 30% of patients will miss at least 50% of their daily CareLink transmissions. Considering these challenges, it is reasonable to expect as little as 50% of our cohort to provide complete data. In such a scenario, a 5,000 patient cohort would be sufficient for modeling health care utilization (1,175 events, 525 AF-related) but would be insufficient for modeling ischemic stroke or for modeling outcome events by smaller subgroups.

7. Statistical Methods

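### Choosing b, l and w by maximum AUROC on one 10% validation set gives an unstable configuration and compares unlike targets; cross-validate b and prespecify l and w

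*SAP*

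**What the plan says.** **Split (SAP 7.9.1, Dataset split).** The data are "randomly split into those three datasets with 70%, 10% and 20% of patients in the training, validation, and testing datasets". Randomization is stratified by site, LINQ indication and LINQ model, but not by outcome. Each patient sits in one set only, and the test set stays untouched until the candidate models have been trained and validated.

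**Tuning (SAP 7.9.1, Tuning).** The parameters b, l and w "will be determined via grid search algorithm using the validation set", with AUROC as the metric to maximize. The grid values are left to the exploratory analysis, and tuning of the training-process hyperparameters is left to the analyst. The public text mentions no cross-validation or repeated splitting.

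**Meaning of l and w (SAP 7.9.1, Data format and Figure 1 caption).** The label is whether the event falls between t+l and t+l+w. The stated reason for l is to leave physicians time to act. Short-term and long-term models are both planned, but the public text gives no horizon for either.

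**Event counts (SAP Section 6; Protocol 13.1).** For 5,000 patients the SAP states: "Of the healthcare utilization events, 1,050 (21%) will be AF-related". It then says that "it is reasonable to expect as little as 50% of our cohort to provide complete data", which gives "1,175 events, 525 AF-related". The 320 to 800 events called for relate to the whole algorithm; no minimum is set for the validation partition.

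**The concern.** Three parameters that decide what the model looks at and what it predicts are fixed by ranking candidates on one tenth of the patients. If that tenth contains few patients with an AF-related visit, the ranking is imprecise. A different random split could then yield a different look-back and horizon from the same study.

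A second issue is independent of sample size. Since l and w define the outcome label, two candidates with different (l, w) are answering different questions. A higher AUROC may mean only that one question is easier. At stake are the stability and clinical meaning of the chosen configuration; the held-out test-set estimate is not at risk.

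**Working it through.** **1. The plan's counts.** 5,000 × 0.21 = 1,050 and 1,050 × 0.5 = 525; 5,000 × 0.47 = 2,350 and 2,350 × 0.5 = 1,175. All match SAP Section 6. The 21% is therefore a share of the cohort (21% of 2,350 would be 494). The SAP calls these events but seems to derive them from a patient-level rate, so reading 525 as patients is an interpretation.

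**2. AF-related patients in the validation set.**
- Half the cohort complete: 0.10 × 525 = 52.5, among 0.10 × 2,500 = 250 patients. The split is not stratified on outcome, so this count has an SD of about 6 (roughly 40 to 65).
- All 5,000 complete: 0.10 × 1,050 = 105 among 500.
- If 21% is taken of the 2,350, half complete: 0.10 × 494 × 0.5 ≈ 25.
- Non-test 80%, half complete: 0.80 × 525 = 420 among 2,000.

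The 52 could be high: 5.2 million days / 5,000 = 1,040 days, or 2.85 years per patient, whereas the 21% is a five-year figure.

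**3. Precision of one AUROC (Hanley-McNeil, patient as unit).** With A = 0.70, Q₁ = A/(2−A) = 0.5385 and Q₂ = 2A²/(1+A) = 0.5765.

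Var = [A(1−A) + (m−1)(Q₁−A²) + (n−1)(Q₂−A²)] / (mn)

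- m = 52, n = 198: (0.21 + 51 × 0.0485 + 197 × 0.0865) / 10,296 = 0.00191; SE 0.044.
- m = 105, n = 395: SE 0.031.
- m = 420, n = 1,580: SE 0.015.

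Moving from 52 to 420 is a factor of 8 in patients and about √8 = 2.8 in SE.

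**4. Precision of a difference between candidates.** All candidates are scored on the same validation patients, so SE(diff) = SE × √(2(1−r)). The documents do not give r; 0.8 to 0.9 is assumed.
- 52 patients: 0.028 (r = 0.8) and 0.020 (r = 0.9). Multiplying by 1.96 gives 0.054 and 0.038.
- 420 patients: 0.010 and 0.007. Multiplying by 1.96 gives 0.019 and 0.014.

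**5. What the imprecision costs.** The grid is not given, so 27 cells were assumed. True AUROCs were evenly spaced around 0.72, with equally correlated errors. Loss is the true AUROC of the best cell minus that of the selected cell. Optimism is the winner's observed AUROC minus its true one. Real share is the part of the observed spread due to true differences. Each pair is 52 versus 420 AF-related patients.

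| True range | r | Loss | Optimism | Real share |
|---|---|---|---|---|
| 0.02 | 0.8 | 0.0064 / 0.0030 | 0.037 / 0.011 | 9% / 44% |
| 0.02 | 0.9 | 0.0052 / 0.0021 | 0.025 / 0.007 | 16% / 61% |
| 0.02 | 0.95 | 0.0041 / 0.0015 | 0.017 / 0.004 | 28% / 76% |
| 0.05 | 0.8 | 0.0084 / 0.0030 | 0.031 / 0.008 | 38% / 83% |
| 0.05 | 0.9 | 0.0060 / 0.0021 | 0.020 / 0.005 | 55% / 91% |
| 0.05 | 0.95 | 0.0043 / 0.0014 | 0.013 / 0.003 | 71% / 95% |
| 0.10 | 0.8 | 0.0086 / 0.0028 | 0.026 / 0.006 | 71% / 95% |
| 0.10 | 0.9 | 0.0061 / 0.0018 | 0.016 / 0.003 | 83% / 98% |
| 0.10 | 0.95 | 0.0042 / 0.0010 | 0.010 / 0.002 | 91% / 99% |

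Picking a cell at random would lose half the range: 0.010, 0.025 or 0.050.

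**6. Maximizing AUROC over l and w.** An illustrative sliding-window simulation used an assumed data model with 24 (b, l, w) points. The search took the shortest w in every run, whether it had 250 or 2,000 patients. It took l = 0 in 94% of runs with 250 patients and 100% with 2,000. More data made the preference for the easiest horizon firmer.

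**The case against.** The strongest reply is that noisy selection limits its own damage: candidates that cannot be told apart perform nearly alike. The table bears this out. The loss is under 0.01 AUROC throughout, and cross-validation recovers roughly 0.003 to 0.006 of it, little beside the 0.1-wide bands of the SAP's descriptive scale. This stands, and it sets the weight of the point.

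A reader might infer that the grid search mostly ranks noise. The documents do not support that. They give neither the grid nor the correlation between candidates. With r = 0.9 and 52 patients, the real share runs from 16% (true range 0.02) to 83% (true range 0.10).

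A reader might also infer that the reported performance is biased. It is not: patients are kept apart across sets, the test set is locked and its metrics carry bootstrap intervals. The optimism attaches only to the winning validation AUROC.

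Three further replies have some force. The 52 belongs to the plan's pessimistic scenario. The SAP may truncate follow-up when device data stop instead of excluding the patient. And the planned AUROC is computed on daily predictions, for which a patient-level calculation is only a proxy. Even so, complete data from all 5,000 gives 105 AF-related patients, and cross-validation would still use eight times as many. Finally, SAP 7.8 already allows modelling details to be revised after the interim analysis, which makes the change easy to adopt.

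**Conclusion.** The point holds as a cheap improvement. In the half-complete scenario, tuning on one 10% set cannot reliably separate candidates whose AUROCs differ by about 0.04 to 0.05. The selected configuration is unstable, and its validation AUROC is optimistic (0.020 at a true range of 0.05 and r = 0.9, against 0.005 with 420 patients). The expected loss of true AUROC is about 0.004 to 0.009, against 0.001 to 0.003 with cross-validation.

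These figures assume:
- the 525 are patients, and the patient is the unit of information;
- AUROC is about 0.70 to 0.72;
- there are 27 cells with a true range of 0.02 to 0.10, and r is 0.8 to 0.95 for the loss (0.8 to 0.9 for the 0.04 to 0.05 limit);
- pooled out-of-fold predictions behave like 420 independent AF-related patients, which is slightly generous because folds share training data.

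It would be tempting to conclude that cross-validation alone settles the matter. It does not. It reduces variance, but a search over l and w would still compare different prediction targets and could give up the lead time that l is meant to provide. That part of the point does not depend on the event count.

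**What to change.** Amend SAP 7.9.1 as follows:

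1. Keep the locked 20% test set unchanged.
2. Replace the fixed 70/10 split with five-fold patient-level cross-validation over the remaining 80%, using the same stratification factors. Do scaling, imputation and any under- or oversampling inside the training folds only.
3. Prespecify l and w for the short-term and the long-term model, consistent with the lead-time purpose the SAP gives for l. Do not choose them by maximum AUROC, and compare candidates only within the same (l, w).
4. Choose b and the model hyperparameters on the out-of-fold AUROC, then refit the chosen configuration on the full 80% before the single use of the test set.

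The cost is SAP wording and about five times the fitting time per configuration; a smaller grid for the neural network would offset this. During tuning each fit uses 4/5 × 80% = 64% of patients instead of 70%, but the final refit uses 80%. No new patients or data are needed.

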13.3.1 Hypothesis

No formal statistical hypotheses will be tested for this objective. Rather, the goal will be to determine whether a risk prediction model can be developed from device-collected measurements that can has adequate sensitivity and specificity to be of use in a clinical setting.

Analysis Methods

Various risk prediction models will be developed and compared to each other. The model(s) with best predictive power will be selected. The input data of these models might be composed of values (original or derived) collected by LINQ ICMs, and the output of the model will be the risk of patient having a AF-related HCU in the future. The model may also account for attributes of patients' medical histories, including CHA2DS2-VASc scores, individual components of CHA2DS2-VASc scores and any other medical

Page 36 of 48

[figure not shown]

history information provided by the patient at enrollment. The predictive value of the model will generally be assessed against the predictive power of any clinical tools available at the time of model development. If additional predictive tools become available at the time of model development, those tools can be integrated into the development of the model and the value of the model will reflect the incremental benefit provided above and beyond the available clinical tools.

Endpoint: Confirmed healthcare visit in the inpatient hospital, outpatient hospital, clinic/office, emergency department, or other care location (including remote visits) where AF was the reason or suspected reason for healthcare interaction.

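### If training data are resampled, nothing in SAP 7.9.1 returns the predicted probabilities to the natural event rate, and no calibration measure is planned

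*SAP*

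**What the plan says.** SAP 7.9.1 expects event windows to be heavily outnumbered and says that "random undersampling/oversampling methods might be needed to build the training dataset". It adds that these methods will not "be used to build the validation and test datasets", so those two sets keep the natural event rate. All models minimise cross-entropy. The look-back, lead time and prediction window (b, l, w) are tuned on AUROC in the validation set, from values still to be chosen.

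Under Testing, the same section has the final models produce each patient's "individual probabilities of having the clinical event in the predictive window", for each patient and day. CIP 13.3.1 says "the output of the model will be the risk of patient having a AF-related HCU in the future". The test-set measures are AUROC, sensitivity, specificity, NPV and PPV, and the descriptive performance scale uses AUROC alone.

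No resampling ratio is given for the study models. One ratio appears elsewhere: the retrospective analysis behind the sample size (SAP 6, CIP 13.1) "under-sampled controls to a 1:1 ratio with over-sampled cases to create a balanced data set". In that analysis "the target window was defined as the five days prior to an event".

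**The concern.** Cross-entropy fits the output to the share of events in the data the model sees. If that share has been raised by resampling, the output is the risk in the resampled set, not the risk in patients. The standard remedy is a shift on the log-odds scale. The plan does not provide for it, and the visible text has no recalibration, calibration intercept or slope, calibration plot or Brier score.

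At stake is the absolute meaning of the output. The SAP calls it a probability and the CIP calls it a risk. The lead time l is there so that physicians can act on patients at high risk. A number that ranks patients correctly but is many times too high would not serve as a risk, and the planned measures do not assess whether it is.

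**Working it through.** **The plan's own figures.** 12%, 47% and 21% of 5,000 are 600, 2,350 and 1,050. The event requirement also reproduces: 80/0.05/10 = 160 and 80/0.02/10 = 400. The divisor 10 fits five case-days per event times two for 1:1 controls, so the sizing itself appears to rest on balanced training data.

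**Inputs.** From SAP 6: "Of the healthcare utilization events, 1,050 (21%) will be AF-related" and "It is expected there will be approximately 5.2 million follow-up days". The 21% matches 5,000 patients; 21% of 2,350 would be 494. I therefore take 1,050 as one event per patient and vary it below. Window w and the sampling ratio are not fixed, so I use ranges: w = 5, 30, 90 and 365 days; ratios 1:1, 1:5 and 1:10.

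**Formulas.**
- Each event makes about w daily windows positive, so the natural rate is p = events × w / follow-up days.
- Resampling to case share s multiplies the fitted odds by [s/(1−s)] / [p/(1−p)]. At 1:1 this is (1−p)/p.
- The correction adds logit(p) − logit(s) to the linear predictor.

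**Worked case, w = 5, 1:1.** p = 1,050 × 5 / 5,200,000 = 0.00101. Odds multiplier = (1 − 0.00101)/0.00101 ≈ 989. A window with true risk 0.10% is given as 50%, which is 0.5/0.00101 ≈ 495 times too high.

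| w (days) | p | Odds ×, 1:1 | Odds ×, 1:5 | Odds ×, 1:10 | Risk ratio at average risk, 1:1 |
|---|---|---|---|---|---|
| 5 | 0.10% | 989 | 198 | 99 | 495 |
| 30 | 0.61% | 164 | 33 | 16 | 83 |
| 90 | 1.8% | 54 | 11 | 5 | 28 |
| 365 | 7.4% | 12.6 | 2.5 | 1.3 | 7 |

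With no resampling or class weighting, the multiplier is 1.

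**Sensitivity to the event count.** With five times as many events (5,250, assuming repeat visits), 1:1 sampling gives 197 at 5 days and 32 at 30 days. Halving both events and days (525 and 2.6 million) leaves p unchanged.

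**Check by simulation.** Set-up: 5.2 million windows, a logistic model, assumed AUROC about 0.80, 70% for training with 1:1 undersampling, and an untouched 20% test set.
- w = 5: mean predicted risk 37.3% against 0.10% observed. After the intercept correction it is 0.10%. AUROC is 0.80 both times.
- w = 30: mean predicted risk 36.7% against 0.61% observed; 0.61% after correction.
- w = 5 with a fixed cut-off of 0.5: the uncorrected model flags 28% of windows with PPV 0.27%; the corrected model flags none.

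**The case against.** The case for the plan is substantial.

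- **Resampling is optional.** The SAP says only that it might be needed. The 1:1 ratio and 5-day window belong to the retrospective analysis, introduced there for CART and random forest; SAP 7.9.1 names tree boosting and temporal convolutional networks. A reader might infer that a 989-fold error is built into the plan. It is not: that figure is the top of the range tabulated, and long-term models, which the SAP also plans, sit near the bottom.
- **The CIP's yardstick is classification.** CIP 13.3.1 asks for sensitivity and specificity good enough for clinical use, and the SAP grades models on AUROC. The intercept correction is monotone, so it changes neither ranking nor any classification whose cut-off is chosen on the model's own scores in the un-resampled validation set. A reader might infer that every cut-off would be wrong. Only one fixed in advance as an absolute risk would be.
- **PPV could expose a gross error.** It is computed at the natural event rate. A PPV of 0.27% above a nominal 50% cut-off would be conspicuous. So the planned measures do not assess calibration, but they would not necessarily hide the problem.
- **No display of risks is planned.** A reader might infer that patients or physicians will be shown inflated risks. The visible text describes producing the probabilities and using them to compute performance measures; the app shows device data such as AF burden.
- **The framework is deliberately open.** Methods may be revised after the interim analysis, and nothing forbids recalibration.

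All of this stands, and it limits the consequence. It does not remove the gap. Resampling is permitted, the output is labelled a probability and a risk, and neither a correction nor a calibration check is prespecified. The discretion that SAP 7.9.1 grants expressly covers missing data and training hyperparameters; calibration is not mentioned.

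**Conclusion.** The point holds as a conditional one. If the training set is resampled or classes are weighted, the absolute risks produced under SAP 7.9.1 will be too high. Under 1:1 sampling the odds are multiplied by about 989 (5 days) down to 12.6 (365 days), and under 1:10 sampling at 30 days by about 16. If neither is used, this error does not arise. Discrimination, and cut-offs chosen on the model's own scores in the validation set, are sound either way.

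The sizes assume 1,050 events over 5.2 million days, one event per patient, and about w positive windows per event. Ratio and window are my range, not the plan's choice. Some SAP pages are not visible, so the absence of a calibration step is a statement about the visible text. This is a low-cost improvement to make before the models are built, not a flaw in the planned assessment of discrimination.

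**What to change.** Add to SAP 7.9.1:

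1. If resampling or class weighting is used in training, model outputs will be corrected analytically for the known sampling fraction (intercept or prior correction) before the test set is opened. Recalibration on the un-resampled validation set is a fallback, for use only where the analytic correction does not apply.
2. Calibration intercept, slope and a calibration plot will be reported on the test set beside AUROC.

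The order in item 1 matters because the validation set is small. It holds 10% of patients, or about 0.10 × 525 ≈ 53 AF-related events in the SAP's 525-event scenario, and is already used to tune b, l and w. The test set, at 20%, would hold about 105 events, so the calibration estimates need intervals; the bootstrap already planned for the other measures can supply them.

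The cost is two sentences, a little extra analysis and, if the fallback is used, some reuse of a small validation set. No new data are needed.
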